#### **4.10.4.      *Electrocardiogram***

Electrocardiogram (ECG) data for each patient will be provided in a data listing.

#### **4.10.5.      *Index Knee X-ray***

Index knee X-rays are performed at Screening for all patients, and at Week 52/End of Study for patients that receive a second injection. The X-rays are read at a central imaging laboratory and are evaluated for joint space narrowing (JSN), subchondral bone changes (SBC), osteonecrosis, and insufficiency fracture at baseline and the end of study. Two independent radiologists will initially read and score each X-ray.

##### **JSN**

Joint space narrowing will be scored in two locations (medial and lateral tibiofemoral compartments) according to the following 4-point ordinal scale of 0 to 3 scale:

0. None: Normal appearance.
1. Mild: Presence of mild narrowing.
2. Moderate: Presence of moderate narrowing.
3. Severe: Presence of severe narrowing

Joint space narrowing for each location will be defined as follows:

- If Reader 1 and Reader 2 agree (are concordant) on the JSN score, then that score will be used in the analysis.
- If Reader 1 and Reader 2 do not agree (are discordant) then the average score of Reader 1 and Reader 2 will be obtained and used in the analysis.

At each visit, the maximum score of the two locations as defined above will be used as the analysis value.

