### 7.4.2. Screening Criteria

#### 7.4.2.1. Screening Inclusion Criteria

To be included in the trial, patients must fulfill the following criteria:

1. Written consent to participate in the study
2. Willingness and ability to comply with the study procedures and visit schedules and ability to follow verbal and written instructions
3. Male or female  $\geq 40$  years of age
4. Symptoms associated with OA of the index knee for  $\geq 6$  months prior to Screening (patient self-report is acceptable)
5. Currently meets ACR Criteria (clinical and radiological) for OA ([Altman et al, 1986](#)) as follows:
  - Knee pain
  - at least 1 of the following:
    - Age  $> 50$  years
    - Stiffness  $< 30$  minutes
    - Crepitus
  - Osteophytes
6. Kellgren-Lawrence (KL) Grade 2, 3 or 4 in the index knee based on X-ray performed during Screening (locally read)
7. WOMAC A total sum score of  $\geq 6$  at Screening and Day 1/Baseline
8. Index knee pain for  $> 15$  days over the last month (as reported by the patient)
9. If bilateral OA exists, pain in the contralateral knee must be less than pain in the index knee as reported by the patient
10. Body mass index (BMI)  $\leq 40$  kg/m^2s
11. Ambulatory and in good general health

12. Willingness to abstain from use of the following protocol-restricted medications during the study:

- Intravenous (IV), intramuscular (IM), and oral corticosteroids (Note: inhaled, intranasal, and topical corticosteroids are allowed)
- IA corticosteroids in any joint
- IA viscosupplementation (hyaluronic acid) or any IA intervention (IA injection, IA aspiration, etc.) in the index knee
- Opiates
- Any investigational drug, device, or biologic
- Immunomodulators, immunosuppressives, or chemotherapeutic agents
- Live or live attenuated vaccines

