## 7.7. Study Variables

### 7.7.1. Safety Variables

Safety and tolerability will be evaluated on the basis of AEs spontaneously reported by the patient or discovered by the Investigator and findings from the following assessments: physical examinations, index knee assessments, vital signs, and clinical laboratory evaluations. In addition the index knee will be evaluated by X-ray and assessed by a central imaging vendor for joint space narrowing, chondrolysis, subchondral bone changes, bone infarcts, avascular necrosis, joint swelling, and insufficiency fracture.

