#### Kellgren-Lawrence Grade of Knee X-ray

- Grade 0: no findings
- Grade 1: doubtful narrowing of joint space and possible osteophytic lipping
- Grade 2: definite osteophytes and possible narrowing of joint space
- Grade 3: moderate multiple osteophytes, definite narrowing of joint space and some sclerosis and possible deformity of bone ends
- Grade 4: large osteophytes, marked narrowing of joint space, severe sclerosis and definite deformity of bone ends

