## Osteonecrosis and Insufficiency Fracture

Osteonecrosis and insufficiency fracture are each measured on a binary scale as absent or present (0=absent, 1=present) and will be adjudicated as follows:

- If Reader 1 and Reader 2 agree (are concordant) on the score of absent or present, then that score is used in the analysis.
- If Reader 1 and Reader 2 do not agree (are discordant) on the score of absent or present, then the X-ray will be read by a third independent radiologist and scored as absent or present. The adjudicated score will agree with either Reader 1 or Reader 2 and that score will be used in the analysis.

Change from baseline to end of study in JSON score will be presented for two-dose patients by patient group (timing of second dose) and for all two-dose patients combined. Any patients whose serial x-rays demonstrate a  $\geq 2$ -point grade increase in JSON will be categorized as indicating Chondrolysis. The frequency and percentage of Chondrolysis will be presented in a summary table for the PPIP and SP separately.

Shift tables of joint space narrowing, subchondral bone changes, osteonecrosis and insufficiency fracture will be presented for two-dose patients, showing shifts from baseline to the end of study by patient group (timing of second dose) and for all two-dose patients combined. These tables will be presented for the PPIP and SP separately.

These X-ray data for all patients, including results for each reader, will be presented in a by patient listing. A separate listing will present baseline Kellgren-Lawrence (K-L) Grade.

After review of X-ray results additional sensitivity analyses may be performed to better understand imaging results.

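### Chondrolysis is judged on the worse compartment's JSN score at each visit, so a knee starting above grade 1 can never be counted, even if its other compartment loses 2 or 3 grades

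*SAP*

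**What the plan says.** Protocol 7.7.1 makes the index-knee X-ray a safety assessment, with the films "assessed by a central imaging vendor for joint space narrowing, chondrolysis, subchondral bone changes" and other findings. Protocol 7.4.2.1 admits patients with "Kellgren-Lawrence (KL) Grade 2, 3 or 4 in the index knee based on X-ray performed during Screening". Appendix 1 of the protocol describes grade 3 as "moderate multiple osteophytes, definite narrowing of joint space and some sclerosis" and grade 4 as "large osteophytes, marked narrowing of joint space, severe sclerosis and definite deformity of bone ends".

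SAP 4.10.5 (JSN) scores the two tibiofemoral compartments "according to the following 4-point ordinal scale of 0 to 3 scale". When the two readers agree, their score stands. When they disagree, their mean is used, so half grades can occur. The two compartments are then reduced to one number: "At each visit, the maximum score of the two locations as defined above will be used as the analysis value".

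The chondrolysis rule appears later in 4.10.5, under the osteonecrosis and fracture heading. A patient whose serial films show a "grade increase in JSON will be categorized as indicating Chondrolysis" threshold of 2 or more points is counted (the abbreviation printed there is evidently a misprint for JSN). On reporting, "The frequency and percentage of Chondrolysis will be presented in a summary table for the PPIP and SP separately". Neither document defines a change in JSN within a compartment.

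**The concern.** The maximum is taken separately at each visit, before the change is computed. The change therefore need not describe any one compartment, and the worse compartment at baseline sets a floor under the follow-up value. There are two consequences.

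- A knee with a baseline value above 1, including an averaged 1.5, has less than 2 points of room on the scale and cannot meet the threshold.
- A loss of 2 or more grades in the better compartment is lost or shrunk whenever the other compartment already sets the maximum.

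Chondrolysis is a named safety variable, and the primary objective is the safety of a second intra-articular steroid injection. K-L 3 and 4 knees are eligible, so knees with narrowing in one compartment at entry are to be expected. Neither PPIP nor SP excludes a knee for its baseline JSN, so knees that cannot register the event can sit in the denominator. At the planned 100 or so two-dose patients (SAP 4.1), one uncounted case is about 1 percentage point.

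**Working it through.** The documents give no chondrolysis rate to reproduce, so the check is on the rule itself.

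**Inputs** (SAP 4.10.5): two compartments, m and l; grades 0 to 3, with half grades when readers differ; threshold 2 or more.

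**Rules compared**
- SAP: max(m1, l1) − max(m0, l0) ≥ 2
- Per compartment: max(m1 − m0, l1 − l0) ≥ 2

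Here 0 is Screening and 1 is Week 52.

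**Step 1: room on the scale.** The largest possible SAP change is 3 minus the baseline maximum.

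| Baseline maximum | 0 | 0.5 | 1 | 1.5 | 2 | 2.5 | 3 |
|---|---|---|---|---|---|---|---|
| Largest possible change | 3 | 2.5 | 2 | 1.5 | 1 | 0.5 | 0 |

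The threshold can be reached only from a baseline value of 1 or less.

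**Step 2: worked cases** (medial, lateral)
- (2,0) to (2,2): lateral loss 2; SAP change 2 − 2 = 0.
- (2,0) to (2,3): lateral loss 3; SAP change 3 − 2 = 1.
- (3,0) to (3,3): lateral loss 3; SAP change 3 − 3 = 0.
- (1,0) to (1,2): lateral loss 2; SAP change 2 − 1 = 1. A case can be missed even from a baseline value of 1.

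**Step 3: how much is the scale and how much is the rule.** On whole grades there are 4 × 4 = 16 baseline pairs. Those with both compartments at 0 or 1 number 2 × 2 = 4, so 16 − 4 = 12 are blocked under the SAP rule. Of these, 2 × 2 = 4 have both compartments above 1 and could not show a 2-grade rise under any rule. The remaining 12 − 4 = 8 are blocked by the maximum alone.

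**Step 4: patterns with a real compartment loss.** All whole-grade patterns were enumerated in which neither compartment improves and at least one loses 2 or more grades.

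| Baseline maximum | Patterns | Missed by SAP rule |
|---|---|---|
| 0 | 12 | 0 |
| 1 | 21 | 4 |
| 2 | 12 | 12 |
| 3 | 6 | 6 |
| Total | 51 | 22 |

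Of the 22 missed, 14 still show a 1-grade worsening and 8 show no change at all. If the other compartment is allowed to improve, 54 of 87 are missed.

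**Step 5: half grades.** With averaged reads and no improvement, 120 patterns start above 1 and the SAP rule flags none. Another 180 start at 1 or below and it flags 148.

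**Step 6: direction.** No pattern on either grid is flagged by the SAP rule but not by the per-compartment rule.

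**The case against.** **The wording.** The chondrolysis sentence speaks of serial films showing an increase and does not say which score it uses; a score for each location is defined before the maximum. A per-compartment reading is therefore conceivable. But the maximum is what the SAP names as the value to analyse at each visit, so it is the natural reading. If the other was meant, the text still needs to say so.

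**The reference.** Neither document defines chondrolysis per compartment, and a rise of 2 in the maximum always implies a rise of 2 in some compartment. The one-way error is thus built into the comparison. That is true, but a 2- or 3-grade loss in a compartment that was scored should not vanish from a safety count because the other compartment was already narrow.

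**Rarity.** In the earlier Phase 3 study (Protocol 5.2.8), 7 + 6 + 5 = 18 of 140 + 148 + 145 = 433 patients with both films worsened by at least 1 grade. Only 1 of the 433 worsened by 2 grades, and that patient was on placebo. Few patients may be affected. However, follow-up was 24 weeks rather than 52, and the protocol does not say how compartments were combined there. When counts are this small, one hidden case matters more.

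**Mitigation.** Each reader's results are listed by patient, and further imaging sensitivity analyses are allowed. A careful reader could find a case, but the analyses are optional and unspecified, and the chondrolysis table would still omit it.

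**Limits of the alternative.** Two compartments give two chances for a reading error to cross the threshold. A knee at (3,0) can register an event in only one compartment. These points stand and belong in the reporting.

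**Conclusion.** The concern holds. Under the only JSN analysis value that the SAP defines, no knee with a baseline value above 1 can be recorded as chondrolysis. A loss of 2 or more grades in the better compartment can be reduced to 1 grade or to none. The scale ceiling explains only part of this: 4 of the 12 blocked whole-grade baseline pairs.

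The direction is certain relative to a per-compartment definition: the planned count can be too low but never too high. The size in patients is unknown. The pattern counts give every score path equal weight and are not frequencies, and 2-grade changes may be rare. The conclusion rests on reading the chondrolysis threshold as applying to the per-visit maximum. It should be fixed, because the safety table would otherwise report a figure that some knees could never contribute to.

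**What to change.** Amend SAP 4.10.5 as follows.

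1. State which score drives the chondrolysis rule, and correct the misprinted abbreviation to JSN.
2. Compute the JSN change within each compartment from the reader-combined scores already defined, and use the larger compartment change as the patient's value.
3. Flag chondrolysis if either compartment rises by 2 or more.
4. Report the number of knees with both compartments above 1 at baseline as not evaluable on this scale, and the number with only one compartment able to register the event.
5. Give the percentage among evaluable knees beside the planned PPIP and SP percentages.
6. Keep the maximum-based shift table as supportive, with a note that the larger compartment change need not equal the difference between its baseline and end-of-study values.

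The cost is SAP text and programming. Compartment scores are already collected at both visits, and no extra reads are needed. The downside is a possibly higher reported chondrolysis rate, part of which may be reading error.

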## SBC

SBC will be derived by determining the presence/absence (0=absent, 1=present) of sclerosis and/or bone attrition in each of four locations (medial femur, lateral femur, medial tibia and lateral tibia). SBC will be presented overall, rather than by category or location and will be derived as follows:

- For each of the 8 possible categories/locations, (sclerosis and bone attrition at each of four locations):
  - If Reader 1 and Reader 2 agree (are concordant) on the SBC score, then that score will be used in the analysis.
  - If Reader 1 and Reader 2 do not agree (are discordant) on the SBC score, then a score of 0 (absent) will be used in the analysis.

If any of the 8 categories/locations are 1 (present), then the SBC will be considered present. It will be considered 0 (absent) only if all of the parameters are 0 (absent).

## Osteonecrosis and Insufficiency Fracture

Osteonecrosis and insufficiency fracture are each measured on a binary scale as absent or present (0=absent, 1=present) and will be adjudicated as follows:

- If Reader 1 and Reader 2 agree (are concordant) on the score of absent or present, then that score is used in the analysis.
- If Reader 1 and Reader 2 do not agree (are discordant) on the score of absent or present, then the X-ray will be read by a third independent radiologist and scored as absent or present. The adjudicated score will agree with either Reader 1 or Reader 2 and that score will be used in the analysis.

Change from baseline to end of study in JSON score will be presented for two-dose patients by patient group (timing of second dose) and for all two-dose patients combined. Any patients whose serial x-rays demonstrate a  $\geq 2$ -point grade increase in JSON will be categorized as indicating Chondrolysis. The frequency and percentage of Chondrolysis will be presented in a summary table for the PPIP and SP separately.

Shift tables of joint space narrowing, subchondral bone changes, osteonecrosis and insufficiency fracture will be presented for two-dose patients, showing shifts from baseline to the end of study by patient group (timing of second dose) and for all two-dose patients combined. These tables will be presented for the PPIP and SP separately.

These X-ray data for all patients, including results for each reader, will be presented in a by patient listing. A separate listing will present baseline Kellgren-Lawrence (K-L) Grade.

After review of X-ray results additional sensitivity analyses may be performed to better understand imaging results.

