**Table 1: Schedule of Study Assessments**

Procedures	Screen 	Baseline Day 1	Week 4 	Week 8 	Week 12, 16, 20, 24 	Week 28, 32, 36, 40, 44, 48 	Week 52  /End of Study
Informed consent	X 						
Inclusion/Exclusion Review	X	X 					
Medical History/Update	X	X 					
OA Medical History	X						
Prior Treatment & Medications	X 	X 					
Physical Examination	X				X 		X
Index Knee X-ray 	X						X 
Index Knee Assessment 	X	X 			X 		X
12-Lead ECG	X						
Vital Signs	X	X 			X 		X
Height	X						
Weight and BMI	X						X
Hematology & Chemistry 	X				X 		X
HIV, Hepatitis B/C 	X						
Serum Pregnancy Test 	X						
Urine Pregnancy Test 		X 			X 		X
WOMAC 	X	X 	X	X	X	X	X
KOOS QOL 		X 	X	X	X	X	X
GPAQ 		X 			X 		
Measured Function Device 			X				
Index knee aspiration and collection of synovial fluid		X 			X 		
1 st treatment administration		X					
Evaluation for repeat administration					X		
2 nd (repeat) treatment administration					X 		
AEs & ConMeds 					X		

 Screening period is a minimum of 7 days, up to 21 days.

 Visit should be conducted within +/- 7 days from scheduled date.

 Consent must be obtained prior to any study-specific procedures.

 Complete assessment prior to dosing.

 Record any prior medications received within 30 days prior to the Screening visit.

 To be completed prior to dosing only if patient is to receive the 2nd dose of FX006. For patients not eligible to receive 2nd dose, complete at the final study visit.

 Standing, fixed flexion PA view, weight bearing X-ray of the index knee will be taken using a standardized knee positioning device. The Screening X-ray will be read locally for K-L grade. The Screening and Week 52 X-rays will be sent to central imaging vendor for safety assessment.

 End of Study x-ray will only be performed if patient has received a repeat administration of FX006.

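### The chondrolysis criterion (a JSN rise of 2 or more, on a value capped at 3) cannot be met by a knee starting above 1, and the planned percentage has no at-risk denominator

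*SAP*

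**What the plan says.** SAP 4.10.5 scores joint space narrowing in the medial and lateral compartments on a "4-point ordinal scale of 0 to 3 scale". When the two readers disagree on a compartment, "then the average score of Reader 1 and Reader 2 will be obtained and used in the analysis", so half-grades can occur. The compartments are then combined: "At each visit, the maximum score of the two locations as defined above will be used as the analysis value".

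A rise of 2 or more between serial films is labelled chondrolysis, in the sentence containing "point grade increase in JSON will be categorized as indicating Chondrolysis". The SAP then says "The frequency and percentage of Chondrolysis will be presented in a summary table for the PPIP and SP separately". It states no denominator, and nothing limits the table to knees that still have room to rise by 2.

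The PPIP (SAP 3.1) needs quantifiable films at baseline and Week 52/End of Study but sets no limit on baseline JSN. The SP is every treated patient. Protocol 7.4.2.1 admits "Kellgren-Lawrence (KL) Grade 2, 3 or 4 in the index knee". Protocol Appendix 1 describes K-L 3 by definite narrowing and K-L 4 by marked narrowing. Footnote 8 to Protocol Table 1 adds "End of Study x-ray will only be performed if patient has received a repeat administration of FX006".

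**The concern.** Chondrolysis is one of the X-ray findings listed as safety variables in Protocol 7.7.1, in a study whose primary objective is the safety of repeat dosing. A zero or low percentage will be read as reassurance about all imaged knees. If some of those knees already sit too high on the scale to record the event, they add to the denominator and can add nothing to the numerator. The percentage then says less than it appears to, and it is silent about the knees with the most narrowing at entry.

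Few or no cases is a realistic outcome. Protocol 5.2.8 reports, for the earlier single-dose Phase 3 trial, 140 + 148 + 145 = 433 patients with films at baseline and Week 24. Only one had a 2-grade worsening, and that knee started at grade 0. With so few events, the denominator determines what the result can support.

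**Working it through.** **Plan's own figure.** Protocol 9.3 and SAP 4.1 expect 200 × 0.66 × 0.75 = 99 two-dose patients to reach Week 52, which matches the stated target of about 100. The documents give no planning figure for chondrolysis.

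**Step 1: who can be a case.** The largest possible rise is 3 minus baseline, and the criterion needs at least 2.

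| Baseline analysis value | Largest rise | Can be a case |
|---|---|---|
| 0 | 3 | yes |
| 0.5 | 2.5 | yes |
| 1 | 2 | yes |
| 1.5 | 1.5 | no |
| 2 | 1 | no |
| 2.5 | 0.5 | no |
| 3 | 0 | no |

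The limit is therefore a baseline of 1. The half-grade 1.5 is also excluded; it arises when the readers score 1 and 2, or 0 and 3.

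**Step 2: number of paired films.** SAP section 5 reports that more than 90% of enrolled patients received a second dose. Using 90% with the planned 75% completion gives 200 × 0.90 × 0.75 = 135. This mixes an observed share with a planning assumption, so it is only a working size.

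**Step 3: effect on a zero-event result.** The share of knees with a baseline of 1 or less is not in the documents; 30%, 50% and 70% are assumptions. The one-sided 95% upper bound with 0 events in n is 1 − 0.05^(1/n). The upper limit of a two-sided exact 95% CI is 1 − 0.025^(1/n).

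| Denominator | n | One-sided 95% bound | Two-sided 95% upper limit |
|---|---|---|---|
| All paired films | 135 | 2.2% | 2.7% |
| 70% at risk | 94 | 3.1% | 3.8% |
| 50% at risk | 67 | 4.4% | 5.4% |
| 30% at risk | 40 | 7.2% | 8.8% |

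On a round 100 films, close to the original planning figure, the one-sided bound is 2.95% for all films, 4.19% for 70 at risk and 5.82% for 50 at risk.

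**Step 4: effect on the percentage.** The all-film percentage equals the at-risk percentage multiplied by the share at risk. Two cases would show as 2/135 = 1.5% of all films, but 2/94 = 2.1%, 2/67 = 3.0% or 2/40 = 5.0% of the knees that could have had the event. The two agree only if no knee starts above 1.

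**The case against.** The strongest reply is that the information is not lost. SAP 4.10.5 plans JSN shift tables for two-dose patients, from baseline to end of study, by timing of second dose and combined, for the PPIP and SP. It also plans change from baseline and a by-patient listing with each reader's score. From these a careful reader could count the knees that started above 1, see which worsened and rebuild the denominator. This stands, and it limits the defect to the headline percentage. That line would still not say how many knees could have met the criterion.

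The all-film percentage is also a legitimate descriptive quantity. The earlier trial reported JSN worsening over all paired films without a baseline restriction. This is a reason to keep it, and it does not stand in the way of an at-risk figure beside it.

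The ceiling applies only to this X-ray label. Subchondral bone changes, osteonecrosis and insufficiency fracture are scored separately, and new or worsened index-knee findings are recorded as AEs. It also depends on the maximum rule: judged per compartment, a knee at medial 2 and lateral 0 could still become a case. The SAP, however, names the maximum as the analysis value.

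A reader might go further and infer that patients without a follow-up film will be counted as event-free in the SP. The documents do not show that. The PPIP already requires both films, SAP 4.2.1 gives categorical tables a missing-data category, and the criterion refers to serial films. The adjoining JSN analyses are limited to two-dose patients, and SAP section 5 puts one-dose patients at about 10. Early termination visits follow the Week 52 schedule (Protocol 7.4.4), so some early leavers may have a film.

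**Conclusion.** The concern holds for the headline percentage. By the SAP's own scale, averaging rule and maximum rule, a knee with a baseline value above 1 cannot be a chondrolysis case, and neither the PPIP nor the SP removes it. That such knees count as event-free is the plain reading of the population definitions; the SAP does not say so outright.

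The size is conditional. With about 135 paired films and an assumed 30% to 70% at risk, the zero-event one-sided 95% bound is 7.2% to 3.1%, against 2.2% on all films.

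Two stronger statements are tempting but unsupported. One is that a large part of the trial starts above the limit. The documents give no K-L distribution and no mapping from K-L to JSN. K-L for entry is read locally and JSN centrally, and definite narrowing is compatible with JSN grade 1. The other is that the SAP plans an upper bound that is too small. It plans only a frequency and percentage here, so the bounds above show what a reader could conclude and do not correct a planned figure.

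**What to change.** In the chondrolysis table of SAP 4.10.5:

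- Keep the planned all-film percentage.
- Add the percentage among two-dose patients with both films and a baseline JSN analysis value of 1 or less, with the number at risk and an exact 95% CI.
- Put knees with a baseline above 1 on their own row, labelled as not able to meet the criterion. Show any worsening of 1 grade or more and progression to grade 3, taken from the planned shift tables. Those tables should keep half-grades separate so that 1 and 1.5 can be told apart. Note how many of these knees start at 2.5 or 3, since they cannot worsen by a full grade.
- For the SP version, use patients with both films as the denominator and show those without a follow-up film as missing. This only clarifies what the PPIP definition and the missing-data category already suggest.
- Correct the misprinted abbreviation to JSN.

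The cost is SAP wording and one revised table from reads already planned, with no new data. The reported rate and its bound become less favourable.
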